$$H_0: \mu_{\Delta} \leq -10\% \text{ versus } H_1: \mu_{\Delta} > -10\%$$

Demonstrating that the mean difference, μ_{Δ} , is greater than -10 percentage points for all three test conditions will be considered to have shown that M90 is non-inferior to Q90. For both cohorts, previous data supported 6.24% SD for the primary efficacy endpoint (labelled 1 below) and 6.61% SD for the first secondary efficacy endpoint (labelled 2 below). As shown in Table X below, there is >90% power per cohort and per endpoint (power columns) to rule out a -10% null hypothesis supporting non-inferiority (N-I) for a one-sided 2.5% test with statistical significance (one-sided $p=0.025$) achieved when <-4.98% and <-4.64% paired mean disadvantages are observed while superiority (reach one-sided $p=0.025$) would be achieved if >5.02% and >5.32% paired mean advantages are observed. The calculations below are based on 8 complete pairs per cohort; a total of 12 pairs will be enrolled in order to accommodate up to four losses per cohort.

Table 4: Paired t-tests to reject the null hypotheses for non-inferiority and superiority

	Power		Reach N-I		Reach Sup	
	1	2	1	2	1	2
Test significance level, α	0.025	0.025	0.025	0.025	0.025	0.025
Null hypothesis mean difference, μ_0	0%	0%	-4.98%	-4.64%	0%	0%
Alternative mean difference, μ_A	-10%	-10%	-10%	-10%	-5.02%	-5.32%
Paired SD, σ	6.24%	6.61%	6.24%	6.61%	6.24%	6.61%
Effect size, $\delta = \mu_A - \mu_0 / \sigma$	1.603	1.513	0.805	0.810	0.804	0.805
Power (%)	94	90	NA	NA	NA	NA
N pairs	8	8	8	8	8	8

These calculations are based on the T-distribution non-centrality factor as follows:

$$T_{n,NCF} = \frac{\sqrt{n}(\mu_A - \mu_0)}{\sigma}$$

observed based on the non-centrality factor:

$$Power = T_{n-1}(T_{n-1}^{-1}(0.95), n - 1, \delta = T_{n,NCF})$$

The sample size (16) can provide sufficient data for determining the safety and reliability of the new strategy. Based on a sample size of 24, the upper bound of the exact event rate was calculated in order to provide complication rates. If no events are observed in 16 subjects, then 15.3% is the upper bound for a one-sided 95% confidence interval on this event rate. This bound provides assurance that events not observed will appear in less than 17.1% of subjects.

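### Section 9.1.2's safety bound, significance cut-offs, power figures and power formula do not follow from the inputs the section states

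*Combined protocol and SAP*

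**What the plan says.** All the figures at issue are in Section 9.1.2 (Sample Size Justification), in the text, Table 4, the power formula and the closing safety paragraph.

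- **Safety.** The paragraph opens with 16: "The sample size (16) can provide sufficient data for determining the safety and reliability of the new strategy". It then changes the number: "Based on a sample size of 24, the upper bound of the exact event rate was calculated". It goes on: "If no events are observed in 16 subjects, then 15.3% is the upper bound for a one-sided 95% confidence interval on this event rate". The last sentence reads: "This bound provides assurance that events not observed will appear in less than 17.1% of subjects".
- **Cut-offs.** For a one-sided 2.5% test with 8 complete pairs, significance for non-inferiority is said to be "achieved when <-4.98% and <-4.64% paired mean disadvantages are observed while superiority" (at one-sided p = 0.025) "would be achieved if >5.02% and >5.32% paired mean advantages are observed".
- **Power.** The text says "there is >90% power per cohort and per endpoint". Table 4 prints 94% for the primary endpoint and 90% for the first secondary endpoint.
- **Formula.** Power is written as a noncentral t distribution function evaluated at the 0.95 quantile of t, with no one-minus in front.
- **Table 4 labels.** In the power columns the row "Null hypothesis mean difference" shows 0% and the alternative shows -10%. The superiority columns show the advantages with a negative sign.
- **Alpha.** Section 9.1.1.1 gives one-sided 0.05 for the primary test. Section 9.1.1.2 sets 0.025 per cohort, and Table 4 uses 0.025 in every column.

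**The concern.** The safety paragraph contradicts itself on its face: one bound is given two values, and two sample sizes are named for it. The wrong value is the more reassuring one, and it is part of this section's only quantitative safety argument. The four cut-offs are described as observed means that reach significance. If they do not reach it, the text calls non-significant results significant. The formula carries a quantile that belongs to a different alpha from the one in the table beside it, so a reader cannot regenerate the table. Power, thresholds and safety precision are the figures this section offers to justify the sample size, so they should be reproducible from the inputs printed with them.

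**Working it through.** **Inputs (Section 9.1.2).** 8 complete pairs, so 7 df; one-sided alpha 0.025; paired SD 6.24% (endpoint 1) and 6.61% (endpoint 2); margin -10 points; true difference 0 for power. Standard errors: 6.24/√8 = 2.206 and 6.61/√8 = 2.337.

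**1. Zero-event bound.** The exact one-sided 95% upper bound for 0 of n is 1 - 0.05^(1/n).

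| n | Bound |
|---|---|
| 16 | 17.07% |
| 18 | 15.33% |
| 24 | 11.73% |

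The 17.1% in the last sentence is reproduced with n = 16. The 15.3% needs n = 18, a number the section never uses. As a bound for 0 of 16, 15.3% carries confidence 1 - (1 - 0.153)^16 = 93.0%, not 95%.

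**2. Cut-offs.** The t statistic is the distance from the null divided by the standard error.

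| Column | Stated mean | Distance from null | t | One-sided p, 7 df |
|---|---|---|---|---|
| Non-inferiority 1 | -4.98 | 5.02 | 2.275 | 0.0285 |
| Non-inferiority 2 | -4.64 | 5.36 | 2.294 | 0.0278 |
| Superiority 1 | +5.02 | 5.02 | 2.275 | 0.0285 |
| Superiority 2 | +5.32 | 5.32 | 2.276 | 0.0285 |

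None reaches 0.025. The distance required is t(0.975, 7) × SE, with t(0.975, 7) = 2.3646: 5.217 for endpoint 1 and 5.526 for endpoint 2. The cut-offs are therefore -10 + 5.217 = -4.78, -10 + 5.526 = -4.47, +5.22 and +5.53. The effect size is 2.3646/√8 = 0.836, against 0.804 to 0.810 in Table 4.

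A likely source is the true difference that gives 50% power at 8 pairs and 0.025. That is 0.804 SD, or 5.02 and 5.31 points. The stated distances have power 50.1% (5.02), 50.7% (5.36) and 50.1% (5.32).

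One-sided 0.05 does not explain them either. It gives distances of 4.18 and 4.43, so cut-offs of -5.82/-5.57 and +4.18/+4.43.

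**3. Power.** Table 4's effect sizes reproduce: 10/6.24 = 1.603 and 10/6.61 = 1.513. The noncentrality is √8 × 10/SD = 4.533 and 4.279. The upper tail of the noncentral t (7 df) beyond 2.3646 is 0.9709 and 0.9539, so power is 97.1% and 95.4% against the printed 94% and 90%.

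Two variants come close: 7 pairs (93.9%/91.2%) and one-sided 0.0125 with 8 pairs (92.3%/89.0%). Neither gives both printed figures after rounding, and each contradicts a stated input.

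**4. Formula, 8 pairs.**

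| Reading | Endpoint 1 | Endpoint 2 |
|---|---|---|
| As printed (0.95 quantile, cumulative), positive noncentrality | 0.8% | 1.5% |
| As printed, with Table 4's signs (negative noncentrality) | about 100% | about 100% |
| 0.95 quantile, with complement | 99.2% | 98.5% |
| 0.975 quantile, no complement | 2.9% | 4.6% |
| 0.975 quantile, with complement | 97.1% | 95.4% |

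No reading returns 94/90. Both the quantile and the complement need correcting.

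**5. Dependence on the number of pairs.** With 9 pairs at the planning SD, the stated means do pass: p = 0.021 for each (0.0211 at -4.98, 0.0205 at -4.64, 0.0211 at +5.02 and at +5.32). With all 12 pairs the distances are 3.965 and 4.200, so the cut-offs are -6.04/-5.80 and +3.96/+4.20.

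**The case against.** The strongest reply is that little depends on these figures. The claim of more than 90% power is true, and the table errs on the conservative side. The cut-offs are never applied: Section 9.1.1.1 specifies a paired t-test, which uses the observed SD and the actual number of pairs. The right safety bound is already printed one sentence after the wrong one. The cut-offs also have an intelligible origin as 50%-power effects, so the fault there is mainly one of labelling. All of this stands, and it limits the consequences. It does not make the figures right: a difference with 50% power is not an observed mean that reaches p = 0.025, which is how the text describes it.

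A second reply concerns the safety denominator. Sixteen equals two cohorts of 8 complete efficacy pairs. Section 6.3 expects up to 24 subjects to be fitted, and Sections 6.1 and 11.0 record adverse events from consent until two weeks after completion or the last visit. Subjects lost to the efficacy analysis may therefore still contribute safety data, and 24 may have been meant. This also stands. The paragraph uses 16 twice and prints the matching 17.1%, so 16 is the smaller edit, but the sponsor has to say which denominator is intended.

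Third, the two alpha values are a Type I error matter and not arithmetic. That is fair, and Section 9.1.1.2 explains why 0.025 applies per cohort. The conflict belongs here because the 0.95 quantile in the formula matches the 0.05 still printed in Section 9.1.1.1. Table 4's reversed labels and signs are presentation only.

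**Conclusion.** The concern holds. On the section's stated inputs:

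- The zero-event bound for 16 subjects is 17.1%, so the stated 15.3% is too low by 1.8 points (17.1 - 15.3). For 24 subjects it is 11.7%.
- The four cut-offs at 8 pairs should be 0.17 to 0.21 points stricter. An observed mean between -4.98 and -4.78 on the primary endpoint, at exactly 8 pairs and the planning SD, is described as significant but is not.
- Power is understated by about 3 and 5 points.
- The printed formula cannot produce the printed power.

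These results assume the exact binomial bound, the paired t-test with 7 df, and the planning SDs. The choice of test, the design, the 12 subjects per cohort and the adequacy of power are unaffected. This should be corrected, but it does not threaten the trial's conclusions.

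**What to change.** 1. **Safety paragraph.** Replace 15.3% with 17.1% and change the sample size of 24 to 16. If all 24 fitted subjects are meant, use 24 with 11.7% throughout.
2. **Cut-offs.** In the text and Table 4, give -4.78/-4.47 and +5.22/+5.53 with effect size 0.836 in all four columns. Label them as values the observed mean difference must exceed if 8 pairs complete and the SD equals the planning value. Alternatively, delete them.
3. **Power.** Replace 94/90 with 97/95.
4. **Formula.** Write Power = 1 - F(t(0.975, n-1); n-1, ncp), where F is the cumulative noncentral t, t(0.975, n-1) is the central t quantile, ncp = √n(μ_A - μ_0)/σ, μ_0 = -10% and μ_A = 0%.
5. **Table 4 labels.** Power columns: null -10%, alternative 0%. Non-inferiority columns: null -10%, observed mean -4.78%/-4.47%. Superiority columns: null 0%, observed mean +5.22%/+5.53%.
6. **Alpha.** Reconcile the one-sided 0.05 in Section 9.1.1.1 with the 0.025 per cohort in Sections 9.1.1.2 and 9.1.2. The figures in items 2 to 4 are for 0.025.

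The cost is a correction to text, table and formula. Design, sample size and choice of test do not change, and stating 0.025 in Section 9.1.1.1 only applies what Section 9.1.1.2 already sets.

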10.0 Safety Measures

The primary safety objective is to evaluate whether there are adverse events related to use of AutoSense or the M90 processor that impact device safety.

11.0 Adverse Event Reporting and Assessment

An adverse event (AE) is defined as any undesirable clinical occurrence experienced by a study subject when using the HiResolution System or when undergoing research procedures, whether or not the AE is considered to be device-related. The definition of an AE also includes any event related to any study procedures or to any underlying medical condition present at baseline that increases in severity during the study. An underlying medical condition that was present at the time of enrollment will not be reported as an AE, but any increase in severity during the study will be reported as an AE.

All device-related and non-device-related adverse events (AEs) will be tracked and reported accordingly throughout the study as defined above in the investigational plan and in accordance with requirements of an IDE investigation. The AEs will be recorded and tracked between completion of the informed consent form (signed and dated) and two weeks after the participant's last study visit. The number and percent of all subjects experiencing adverse events

**Evaluation of AutoSense OS on a Naída CI M90 Sound Processor Programmed with Target CI
Fitting Software in Adult Users of the HiResolution Bionic Ear System**

will be summarized by type, status and frequency of event. Adverse Events will be recorded and will include but are not limited to the following information [refer to Appendix B for Case Report Forms (CRFs)]:

11.1.1 Adverse Event Definitions and Classifications

11.1.1.1 Serious Adverse Event

A serious adverse event (SAE) is an event that: a) led to a death, or b) led to a serious deterioration in the health of the subject that:

- resulted in a life-threatening illness or injury,
- resulted in a permanent impairment of a body structure or of a body function,
- required inpatient hospitalization or prolongation of existing hospitalization,
- resulted in medical or surgical intervention to prevent permanent impairment to body structure or a body function, or
- led to fetal distress, fetal death or a congenital abnormality or birth defect.

11.1.1.2 Adverse Device Effect and Serious Adverse Device Effect

An adverse device effect (ADE) is any untoward and unintended response to a medical device. A serious adverse device effect (SADE) is an event related to the device that resulted in any of the consequences characteristic of a serious adverse event (SAE) or that might have led to any of the consequences if suitable action had not been taken or interventions had not been made or if circumstances had been less opportune.

11.1.1.3 Unanticipated Adverse Device Effect

An unanticipated adverse device effect (UADE) is any serious adverse effect on health or safety; any life threatening problem or death caused by, or associated with, a device, if that effect, problem, or death was not previously identified in nature, severity, or degree of incidence in the investigational plan or application; or any other unanticipated serious problem associated with a device that relates to the rights, safety, or welfare of subjects.

11.1.2 Adverse Event Reporting

All adverse events and adverse device effects, serious and non-serious, will be recorded on the Adverse Event Report Case Report Form [CRF] (see Appendix A for all CRFs). Information to be recorded on the CRF should include, but is not limited to:

- Date of onset of the adverse event
- Description of the event, duration and severity
- Seriousness
- Relatedness
- Treatment/Intervention – course of action taken
- Outcome/Status (Resolved, Improved, Stable, Worse, Unchanged). In case of an SAE, the subject must be followed until the serious adverse device effect is resolved or no reasonable improvement is expected.

Evaluation of any SAE, SADE, or UADE will be conducted promptly. Confirmed UADEs will be reported to the FDA according to 21 CFR Part 812.150(b) (1) within 10 days after receiving notice of the event, to participating Investigators and to IRBs according to their requirements. If it is determined that an event or effect presents an unreasonable risk to subjects, this study, or those parts of the study presenting that risk, will be terminated no

Evaluation of AutoSense OS on a Naída CI M90 Sound Processor Programmed with Target CI Fitting Software in Adult Users of the HiResolution Bionic Ear System

later than 5 working days after the determination is made and no later than 15 working days after Advanced Bionics/Clinical Research first received notice of the event.

11.1.3 Anticipated Adverse Events

The risks associated with the investigational products include but are not limited to:

- There is a possibility that speech and environmental sounds may sound different or louder than what the subjects are accustomed to hearing or that subjects may not like the sound quality of AutoSense on the M90 processor. This risk occurs with all changes to sound-processing, and subjects should be advised of this possibility. If a subject cannot tolerate using AutoSense on the M90 processor or does not like the sound quality, they can return to using their own processor with their baseline programming. In this event, the subject will be withdrawn from the study.
- Subjects may experience some overly loud sounds that result in discomfort. If such loud sounds occur, they can be stopped immediately by removing the headpiece and/or the entire external device.
- Subjects may experience neural tissue damage in the event of chronic overstimulation.
- There is risk of facial nerve stimulation. This risk can be mitigated through reprogramming of the device.
- Subjects may experience intermittent sound or short-term loss of functionality while wearing the device or while being programmed. The intermittency can be eliminated by changing the headpiece, reprogramming the processor, or exchanging the processor.
- Subjects may have permanent residual acoustic or natural hearing damage due to excessive acoustic power.
- Subjects may experience skin or tissue irritation because of the device materials or the equipment may overheat or otherwise malfunction, causing tissue damage.
- Subjects will be exposed to small parts that pose a choking hazard. Care should be taken to avoid choking and the outcomes of choking, such as endoscopic surgery or death.
- Exposure to electromagnetic emissions from the device (external sound processor, internal device) may adversely interfere with other electronic medical devices
- Subjects should only use accessories compatible or designed for the M90 processor (such as the battery chargers) in order to avoid electronic shock.
- Static electricity can potentially damage sensitive electronic components such as the ones used in the cochlear implant system.

A complete listing of the risks can be found in Appendix A, all risks listed are considered anticipated Adverse Events. Risks are minimized by device safety testing but cannot be completely eliminated. In these cases, or at any time, subjects may discontinue use of the loaner M90 study processor, and return to using their own processor and baseline program. If subjects stop using the M90 study processor during the study, they will be withdrawn from the study.

In all case, the event(s) will be recorded and the incidence of such events reported as part of the results analysis.

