7.2 Procedures

Audiometric testing and speech perception testing will be conducted in a single- or double-walled sound booth. Audiometers will conform to ANSI standards for pure-tone and speech audiometry and/or Manufacturer Specifications.

Audiometric testing is performed at the Baseline visit to determine eligibility and assignment to the two cohorts. The AzBio Sentence test in quiet and in noise will be used as the test metric to determine primary and secondary endpoints, respectively. In addition, subjects will complete a sponsor developed subjective questionnaire at the baseline visit and at the end of the two week chronic evaluation period.

Evaluation of AutoSense OS on a Naída CI M90 Sound Processor Programmed with Target CI Fitting Software in Adult Users of the HiResolution Bionic Ear System

[figure not shown]

Figure 2. Study Flow Chart

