8.2.2 Follow-Up Self-Assessment Questionnaire

Subjects will complete a custom self-assessment questionnaire on paper or through the EDC system 14 to 21 days after the baseline visit. If completed on paper, the questionnaire will be returned together with the investigational device.

8.2.3 Adverse Event Assessment:

An adverse event assessment is completed by the investigator at the end of the chronic period.

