In the above equation, $b = 2.33$, the percentile of the normal curve corresponding to the desired values of $\alpha = 0.01$, one-tailed test. Using Gifford's σ value, the critical difference score for AzBio sentences is 8.9%.

The number and percentage of subjects exceeding, within, and below the critical difference (Investigational - Control) score will be tabulated. The shift from the baseline assessments will be summarized for both the Experimental and Control results indicating *improved*, the *same*, or *deteriorated*. Further the difference between the two strategies will be evaluated and classified as better for the Experimental strategy, the same for both strategies, or better for the Control strategy. A two-sided exact binomial test will be used to evaluate the null hypothesis that the distribution of subjects showing a performance difference (Investigational is better or Control is better) is distributed equally. This analysis will

Evaluation of AutoSense OS on a Naída CI M90 Sound Processor Programmed with Target CI Fitting Software in Adult Users of the HiResolution Bionic Ear System

provide an additional indication of the efficacy of AutoSense on the M90 processor relative to AutoSound on the Q90 processor based upon individual data.

9.1.1.4 *Safety Endpoint*

The primary safety objective is to evaluate whether there are adverse events related to use of AutoSense OS or the M90 processor that impact device safety.

9.1.1.5 *Supporting Data*

Acceptability questionnaire data will be analyzed descriptively using frequency and percent relative frequency for categorical variables.

9.1.2 *Sample Size Justification*

A total sample size of 12 subjects per cohort is planned for this study based upon efficacy and safety considerations. Previous cohort-specific data were used to estimate the standard deviations (SD) for the paired M90-Q90 differences. The minimum number of subjects required for the study was calculated based upon the primary efficacy outcome measures. The primary efficacy objective is to demonstrate non-inferiority of AutoSense on the M90 processor compared to AutoSound on the Q90 processor for the AzBio sentence test in quiet mode based on a paired t-test. The primary efficacy analyses will test the null hypothesis that the mean of the paired differences (μ_{Δ}) in AzBio sentence scores in quiet mode (AutoSense on M90 – AutoSound on Q90) are less than or equal to -10 percentage points, where:

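### Subjects who stop using the M90 are withdrawn with no exit questionnaire, so the descriptive acceptability summary will by default describe only those who kept the device

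*Combined protocol and SAP*

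**What the plan says.** Section 11.1.3 (Anticipated Adverse Events) opens its list of risks with the possibility that the subject finds the sound different, too loud or unpleasant. The condition is worded "If a subject cannot tolerate using AutoSense on the M90 processor or does not like the sound quality", and the consequence is "In this event, the subject will be withdrawn from the study". The section closes with a general rule covering any reason: "If subjects stop using the M90 study processor during the study, they will be withdrawn from the study". The next sentence requires such events to be recorded and their incidence reported with the results.

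Section 7.2 sets two questionnaire occasions: "at the baseline visit and at the end of the two week chronic evaluation period". Section 8.2.2 fixes the second: "Subjects will complete a custom self-assessment questionnaire on paper or through the EDC system 14 to 21 days after the baseline visit". The table in Section 8.3 shows the same two occasions. No questionnaire at early withdrawal is described.

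Section 9.1.1.5 gives the analysis: "Acceptability questionnaire data will be analyzed descriptively", by counts and percentages. It does not say who is in the denominator. The Synopsis classes the questionnaire as supporting data and ties it to two weeks of use. Section 9.1 also lists the feedback as a subjective endpoint.

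**The concern.** The event that removes a subject from the questionnaire is closely related to what the questionnaire is meant to measure. A subject who dislikes the M90 enough to stop is withdrawn before the form is due, while a subject who likes it reaches day 14 and answers. Missing answers then depend on the answer itself, and the likely direction favours the investigational device.

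All AzBio testing is acute, at the Baseline Visit. Section 6.1 says the two-week period exists to evaluate the device in ordinary life. Apart from adverse events and the processor session documented on return (Section 8.2.1), the questionnaire is the evidence from that period. At stake is how a reader understands everyday acceptability. No efficacy claim depends on it.

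**Working it through.** **Step 1. Can another occasion supply the missing opinion?** The baseline questionnaire (Section 8.1.1) is listed ahead of the M90 fitting (Section 8.1.5), so it would not hold a view of the M90. The remaining occasion is day 14 to 21. A subject withdrawn before then has no scheduled occasion after exposure.

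**Step 2. Does the missing-data text cover it?** Section 9.1.1.1 recognises that some participants may not finish, and mentions the questionnaire period in doing so. It then rules out imputation and applies its repeat analysis to the primary and secondary effectiveness endpoints. The questionnaire is not included.

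**Step 3. Are the efficacy endpoints touched?** No. The paired differences come from baseline testing (Sections 8.1.4 to 8.1.7 and 9.1.1.1), before home use begins (Section 8.2.1).

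**Step 4. The plan's own figure.** Section 9.1.2 needs 8 complete pairs per cohort and allows four losses: 8 / (1 − 4/12) = 12, which reproduces the planned 12. This allowance protects AzBio pairs. It is not a rate of stopping the M90 and is used below only to limit the range shown.

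**Step 5. Hypothetical size.** Inputs:

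- 12 fitted per cohort (Section 9.1.2).
- *w* = subjects who stop early and give no answer (assumed, 1 to 4).
- *p* = proportion of completers who are favourable (assumed).
- Early stoppers are counted as not favourable (assumed).
- Opinion can be reduced to favourable or not (assumed; the questionnaire is not in the documents).

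Completers only: *p*. All fitted: *p* × (12 − *w*)/12. Gap: *p* × *w*/12.

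| *w* | Completers | Completers only, *p* = 1 | All fitted, *p* = 1 | Gap (points) |
|---|---|---|---|---|
| 1 | 11 | 100% | 11/12 = 91.7% | 8.3 |
| 2 | 10 | 100% | 10/12 = 83.3% | 16.7 |
| 3 | 9 | 100% | 9/12 = 75.0% | 25.0 |
| 4 | 8 | 100% | 8/12 = 66.7% | 33.3 |

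With *p* = 0.75 and *w* = 4, the figures are 6/8 = 75% among completers and 6/12 = 50% of those fitted, a gap of 25 points. If nobody stops early, the gap is zero.

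**The case against.** The strongest reply is that these subjects do not disappear. Disliking the sound is itself on the list of anticipated events, Section 11.1.3 requires the incidence of such events to be reported, an adverse event assessment closes the chronic period (Section 8.2.3), and Section 6.5 logs each enrolled subject's disposition. This stands, and it limits the importance of the point. It does not supply their answers or put them beside the acceptability percentages, and the disposition examples in Section 6.5 do not include the reason for leaving.

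A second reply is that the questionnaire is non-standardised supporting data, with no hypothesis, success criterion or place in the testing hierarchy. This also stands. The possible harm is a misleading descriptive percentage.

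A third is that nothing forbids a site from giving the form at withdrawal, and that Section 9.1.1.5 does not state a completers-only analysis. Both are true. The gap is silence. But nothing requires the form either, and practice could differ across up to six sites.

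A reader might also infer from the four-loss allowance that the plan expects up to a third of a cohort to reject the device, so that 66.7% would be the true acceptability. The documents do not support that. The allowance concerns complete AzBio pairs, and a subject who stops at home has normally already contributed one. No discontinuation rate is given, and no single acceptable-or-not item is shown.

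**Conclusion.** The point holds as a gap in data collection and reporting. As written, the plan ties withdrawal to dislike or intolerance, schedules its only questionnaire after exposure for those who remain, and leaves the denominator unstated. By default the summary would describe those who kept the device and would tend to favour it.

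The size is unknown. The 8 to 33 points in the table are hypothetical, and rest on every completer being favourable, every early stopper being counted as not favourable, and one to four stops in a cohort of 12. The gap is smaller if completers are less uniformly favourable or if some early stoppers liked the device.

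It would be wrong to conclude that the plan prescribes a completers-only analysis, that it conceals these subjects, or that the non-inferiority and superiority results are biased. The effect is confined to descriptive supporting data. The change is still worth making, because it is cheap and the answers cannot be reliably recovered after withdrawal.

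**What to change.** Leave the withdrawal rule unchanged.

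- **Section 8.2.2:** add that any fitted subject who stops early and is willing is asked to complete the same questionnaire when returning the device, recording the reason for stopping and the days of use. A subject who withdraws consent cannot be required to answer, so non-response should be recorded as such.
- **Section 9.1.1.5:** state that acceptability is reported by cohort with the number fitted as the denominator. Show early stoppers (answers, reasons, no response) in a separate row beside the two-week completers. Do not pool the two groups, because the questionnaire is defined after two weeks of use and a few days' exposure is not comparable.

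The cost is about one sentence in each section. The form, the electronic entry route and the return envelope already exist (Sections 8.2.2 and 8.2.4). The downside is slightly more data collection and a percentage that may look less favourable.
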